8.1.1 Grades 1 and 2 Toxicity

Participants who develop a Grade 1 or 2 laboratory abnormality or AE may continue the study treatment at the discretion of the site investigator and managed according to local guidelines.

8.1.2 Grade 3 Toxicity

If a participant develops a Grade 3 laboratory abnormality, a confirmatory measurement should be obtained within 5 days after the laboratory result becomes available.

A Grade 3 laboratory abnormality that is not confirmed upon repeat testing will be managed according to the toxicity management guidance for the new toxicity grade.

If the Grade 3 laboratory abnormality is confirmed or the participant has a Grade 3 clinical AE, the study treatment may be continued if the laboratory abnormality or clinical AE is considered to be unrelated to study drug after discussion with the A5415 CMC ([contact]).

If a confirmed Grade 3 laboratory abnormality or an AE is considered to be related to study treatment, the study treatment should be interrupted. The AE should be monitored and/or the laboratory test repeated regularly as clinically indicated. The study treatment may be resumed once the toxicity returns to Grade ≤2.

If a laboratory abnormality or AE recurs to Grade ≥3 following rechallenge with study drug and is considered related to study treatment, the study treatment will be permanently discontinued and the participant managed according to local practice. The decision to continue a participant on study/off study treatment until completion of all other study visits for assessment of clinical outcomes must be agreed upon by the site investigator and the A5415 CMC. Refer to [section 6.2.4](#) for the instructions for following participants on study/off study treatment.

Recurrence of a laboratory abnormality or AE considered unrelated to study treatment may not require permanent treatment discontinuation. Continuing the study drug after a recurrent Grade 3 laboratory abnormality or AE considered not related to study treatment should be discussed with the A5415 CMC ([contact]) prior to continuing the study drug.

The study treatment may be continued without dose interruption for a clinically nonsignificant Grade 3 laboratory abnormality (e.g., glucose elevation in participants with pre-existing diabetes; glucose, cholesterol or triglyceride elevation that is non-fasting or that can be medically managed).

8.1.3 Grade 4 Toxicity

If a participant develops a Grade 4 laboratory abnormality, a confirmatory measurement should be obtained within 5 days after the laboratory result becomes available.

The study treatment may be continued without dose interruption for a clinically nonsignificant Grade 4 laboratory abnormality (e.g., glucose elevation in participants with pre-existing diabetes; glucose, cholesterol, or triglyceride elevation that is non-fasting or that can be medically managed).

A Grade 4 laboratory abnormality that is not confirmed upon repeat testing will be managed according to the toxicity management guidance for the new toxicity grade.

If the Grade 4 laboratory abnormality is confirmed or the participant has a Grade 4 clinical AE, the study treatment may be continued if the laboratory abnormality or clinical AE is considered to be unrelated to study treatment after discussion with the A5415 CMC ([contact]).

If a confirmed Grade 4 laboratory abnormality or an AE is considered to be related to study treatment, the study treatment should be permanently discontinued and the participant managed according to local guidelines. The participant should be followed as clinically indicated until the AE or laboratory abnormality returns to Grade ≤ 2 , if applicable, or is otherwise explained, whichever occurs first.

The decision to continue on study/off study treatment until completion of all other study visits for assessment of clinical outcomes must be agreed upon by the site investigator and the A5415 CMC. Refer to [section 6.2.4](#) for the instructions for following participants on study/off study treatment.

8.2 Specific Management of Toxicities Related to Study-Provided Treatment

8.2.1 Elevated Liver Enzymes

Site personnel must report treatment-emergent (i.e., not present at screening or baseline) and confirmed ALT and/or AST elevations meeting any of the following criteria for suspected drug-induced liver injury (DILI), with special consideration given to baseline transaminase values:

- When the baseline ALT or AST values are $<2 \times$ ULN, and the ALT and/or AST increases to $>3 \times$ ULN and $>5 \times$ the baseline value (confirmed upon repeat testing).

- When the baseline ALT or AST values are $<2 \times$ ULN, and ALT and/or AST increases to $>3 \times$ ULN but $\leq 5 \times$ the baseline value (confirmed upon repeat testing) AND the increase is accompanied by total bilirubin $>2 \times$ ULN (in participants with Gilbert's syndrome use direct bilirubin $>2 \times$ baseline) AND/OR if the participant also has symptoms consistent with clinical hepatitis (for example, fatigue, nausea/vomiting, right upper quadrant [RUQ] abdominal pain or tenderness, fever, rash, or eosinophilia) without an alternative explanation for the event as judged by the site investigator.
- When the baseline values are $\geq 2 \times$ ULN but $<5 \times$ ULN, and the ALT and/or AST increases to $>3 \times$ the baseline value (confirmed upon repeat testing).
- When the baseline values are $\geq 2 \times$ ULN but $<5 \times$ ULN, and the ALT and/or AST increases to $>2 \times$ the baseline but $\leq 3 \times$ baseline value (confirmed upon repeat testing) AND the increase is accompanied by total bilirubin $>2 \times$ ULN (in participants with Gilbert's syndrome use direct bilirubin $>2 \times$ baseline) AND/OR if the participant also has symptoms consistent with clinical hepatitis (e.g., fatigue, nausea/vomiting, RUQ abdominal pain or tenderness, fever, rash, eosinophilia) without an alternative explanation for the event as judged by the site investigator.
- When baseline values are $\geq 5 \times$ ULN and ALT and/or AST increases to $>2 \times$ the baseline value (confirmed upon repeat testing).
- When the ALT and/or AST increases to $>3 \times$ ULN and $>2 \times$ baseline (confirmed upon repeat testing) AND the increase is accompanied by either total bilirubin increase to $>2 \times$ the baseline value OR INR increase by >0.3 from baseline to a value >1.5 .

The participant must return to the CRS for re-evaluation within 5 days after the treatment-emergent AST and/or ALT elevation for confirmatory testing that will include an ALT or AST, AND total bilirubin or INR. A comprehensive clinical evaluation, including evaluations for causes other than study treatment, and close clinical monitoring must be performed. The A5415 CMC should be informed via email ([contact]) within 48 hours of receipt of the treatment-emergent AST and/or ALT elevation.

After the confirmation that the ALT or AST elevations and other laboratory tests meet the criteria for suspected DILI, the A5415 CMC should be informed via email ([contact]) within 48 hours. Study treatment should be interrupted upon confirmation. After consultation with the CMC, a decision regarding temporary or permanent discontinuation will be made. The participant should continue to be followed for close monitoring, which will include repeat liver enzyme and serum bilirubin tests at least once a week, and INR as clinically indicated, until abnormalities stabilize and the participant is asymptomatic. Refer to the A5415 MOPS for additional guidance on evaluating participants with suspected DILI.

Site investigators may involve the CMC in the clinical management of LFT abnormality or clinical hepatitis without other explanation whenever there is concern that the event is study treatment-related, regardless of whether specific DILI criteria are met, to discuss study drug management.

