6.2.3 Post-Entry Evaluations

On-Treatment Evaluations

All post-entry evaluations must be scheduled as per [section 6.1](#).

Weeks 4 through 22 have a visit window of ± 7 days. Week 24 has a visit window of -7 and +14 days.

Study Completion Evaluations

The week 24 evaluations will be the participant's final on-study visit. Participants must continue taking the study treatment until all week 24 evaluations are completed. If needed, study treatment will be extended until the week 24

evaluations are completed. It is encouraged that all week 24 evaluations occur on the same day. If evaluations cannot occur on the same day as the FDG-PET/CT imaging, evaluations must occur ± 7 days of imaging. Site personnel should notify the A5415 CMC via email ([contact]) if study treatment is anticipated to require extension past the week 24 visit window to complete the required evaluations.

Event-Driven Evaluations

Evaluations must be scheduled as per [section 8.0](#).

Confirmation of Suspected Virologic Failure

Virologic failure is defined as two consecutive plasma HIV-1 RNA levels ≥ 200 copies/mL at any visit.

If the HIV-1 RNA level is ≥ 200 copies/mL at any visit, a repeat HIV-1 RNA will be performed (per [section 6.1](#)) within 2 weeks of receipt of the result. If the Confirmation of Suspected Virologic Failure visit coincides with a regularly scheduled visit, the evaluations should be combined. If the repeat HIV-1 RNA level is ≥ 200 copies/mL, the participant will be considered to have confirmed virologic failure and the A5415 CMC must be notified via email CMC ([contact]) within 48 hours.

If a participant is confirmed to have virologic failure, the participant must return to the clinic to complete the premature treatment discontinuation evaluations as described in **section 6.2.4** and then taken off study treatment. If an evaluation is not completed at the premature treatment discontinuation visit, effort should be made to obtain the evaluation as soon as possible and within the evaluation window. The participant will be followed on study/off study treatment through completion of the study.

Confirmation of Grade ≥ 3 Toxicity

Toxicities are defined in [section 8.0](#). Evaluation of Grade ≥ 3 laboratory toxicity must follow instructions outlined in [sections 8.1](#) and [8.2](#). Only the evaluations required to assess the toxicity are required at this visit.

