6.3.5 Laboratory Evaluations

At screening, pre-entry, and entry, all protocol-required laboratory values must be recorded regardless of grade.

For post-entry assessments, record all of the following values regardless of grade:

- Hemoglobin
- White blood cell (WBC) count with differential
- Platelet count
- Creatinine
- Fasting glucose
- HbA1c
- Total cholesterol (fasting)
- HDL cholesterol (fasting)
- LDL cholesterol (fasting)
- Triglycerides (fasting)
- AST
- ALT
- Total bilirubin
- Direct bilirubin
- Prothrombin Time (PT)
- International Normalized Ratio (INR)
- Estimated GFR

NOTE: Refer to the A5415 MOPS for the link to the CKD-Epi equation and calculator.

Refer to [section 7.2](#) for AE reporting requirements for post-entry abnormal laboratory findings.

Refer to the current A5415 Laboratory Processing Chart (LPC) for the collection and processing instructions.

Fasting Instructions

Fasting is defined as nothing to eat or drink except prescription medications and water for at least 8 hours, preferably 10 hours. If participants are in a non-fasting state, they should be instructed to return to the clinic within 3 days of the original scheduled visit for fasting evaluations (as indicated in [section 6.1](#)).

Fasting is NOT required for pregnant participants.

For the fasting requirements for the FDG-PET/CT imaging: See [section 6.3.9](#).

Hematology

Hemoglobin, hematocrit, red blood cells (RBCs), WBCs with differential, absolute neutrophil count (ANC), and platelets

Blood Chemistries

Serum electrolytes (sodium, potassium, and chloride), BUN, creatinine, and amylase.

Fasting Glucose

Fasting blood sample for glucose will be collected per [section 6.1](#). **All glucose collections** should be collected in a gray top tube (sodium fluoride). Refer to the current A5415 LPC for the collection and processing instructions.

Insulin

At screening, fasting blood sample for insulin will be collected and insulin testing will be performed in real time.

After screening, insulin testing will be performed on stored serum (see [sections 3.0](#) and [6.3.8](#)).

Fasting Lipid Panel

Total cholesterol, HDL cholesterol, LDL cholesterol, and triglycerides

Liver Function Tests (LFTs)

AST (SGOT), ALT (SGPT), alkaline phosphatase (ALP), total bilirubin, and direct bilirubin

HbA1C

HbA1c will be done in real-time per [section 6.1](#).

Prothrombin Time (PT) and International Normalized Ratio (INR)

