PT will be performed to support calculation of the INR when needed to confirm elevated liver enzymes that occur on study (see [section 8.2.1](#)).

hsCRP

At screening, hsCRP will be performed in real-time.

After screening, hsCRP will be performed on stored plasma (see [sections 3.0](#) and [6.3.8](#)).

Estimated GFR

GFR will be estimated using the CKD-Epi equation per [section 6.1](#). Refer to the A5415 MOPS for further information and a link to the CKD-Epi equation and calculator.

Pregnancy Testing

For people of childbearing potential: Serum or urine β -HCG at screening and entry. Urine test must have a sensitivity of <25 mIU/mL. The pregnancy test at entry must be performed within 15 days of the visit and the result must be available at the site at the time of entry.

At all other visits, perform as indicated in [section 6.1](#) and if pregnancy is suspected.

In the event of a positive pregnancy test result, refer to [section 8.5](#) for pregnancy and pregnancy outcome reporting requirements.

For pregnancy testing prior to conducting the FDG-PET/CT imaging: See [section 6.3.9](#).

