8.0 CLINICAL MANAGEMENT ISSUES

8.1 Toxicity

Management of abnormal liver enzymes and GFR are explained in [section 8.2](#).

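### The tests required to confirm a liver-enzyme rise can leave the INR route to suspected drug-induced liver injury untested

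*Protocol*

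**What the plan says.** Protocol section 8.2.1 lists six ways for a confirmed, treatment-emergent ALT or AST elevation to count as suspected DILI. In the sixth, the enzyme exceeds both 3×ULN and twice baseline, and either total bilirubin more than doubles from baseline "OR INR increase by >0.3 from baseline to a value" above 1.5.

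The participant returns within 5 days for "confirmatory testing that will include an ALT or AST, AND total bilirubin or INR". Once the criteria are confirmed, "Study treatment should be interrupted upon confirmation". Follow-up then consists of "repeat liver enzyme and serum bilirubin tests at least once a week, and INR as clinically indicated".

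Other sections bear on whether INR is measured:

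- **Section 6.1 (Schedule):** PT/INR is marked at entry. After that it appears only as conditional entries, and the one at the toxicity-confirmation visit refers to section 8.2.1.
- **Section 6.3.5:** the liver panel is "AST (SGOT), ALT (SGPT), alkaline phosphatase (ALP), total bilirubin, and direct bilirubin". On coagulation, "PT will be performed to support calculation of the INR when needed to confirm elevated liver enzymes that occur on study", again with a reference to section 8.2.1.
- **Section 6.2.3:** at the confirmation visit, "Only the evaluations required to assess the toxicity are required at this visit".
- **Section 8.1:** "Management of abnormal liver enzymes and GFR are explained in" section 8.2, so the general Grade 3 and 4 rules defer to section 8.2 for liver enzymes.

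**The concern.** The criteria treat bilirubin and INR as alternative routes to the same conclusion, so ruling out the sixth criterion needs both results. The confirmatory sentence treats them as alternative tests, so one is enough to comply. Where bilirubin is the test chosen, the INR route is never examined.

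Interruption of study drug depends on confirming that the criteria are met. A participant whose only qualifying finding is an INR rise would be recorded as not meeting them and could stay on drug. The matter is relevant to this compound: section 2.1 reports, for the AURORA trial, ALT increases in 3.8% of cenicriviroc participants against 1.5% on placebo, and 4 against 0 participants with possible or probable DILI. All 4 cases were non-serious and resolved after the drug was stopped.

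**Working it through.** The plan gives no figure to reproduce. The check compares the required tests with the criteria, then finds which participants are affected.

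**1. Which test sets comply?** Three do: enzyme plus bilirubin, enzyme plus INR, or enzyme plus both. The first leaves the INR route open. Grouping the sentence the other way, as (enzyme and bilirubin) or INR, does not guarantee an INR either.

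**2. Does another section require INR?** None of the visible text does. The Schedule and section 6.3.5 both point back to section 8.2.1, the liver panel omits INR, and the weekly follow-up that mentions INR starts only after the criteria are met.

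**3. Who is affected?** Let *b* be the baseline enzyme and *x* the confirmed on-treatment value, both in ×ULN. Assume no unexplained hepatitis symptoms, and total bilirubin neither above 2×ULN nor above twice baseline (in Gilbert's syndrome, direct bilirubin also not above twice baseline). Criteria 2 and 4 then cannot be met.

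- *b* < 2: criterion 1 needs *x* > 3 and *x* > 5*b*; criterion 6 needs *x* > 3 and *x* > 2*b*. Only the INR route remains when max(3, 2*b*) < *x* ≤ 5*b*. This range is empty unless 5*b* > 3, that is *b* > 3/5 = 0.6.
- 2 ≤ *b* < 5: criterion 3 needs *x* > 3*b*, so only the INR route remains when 2*b* < *x* ≤ 3*b*.
- *b* ≥ 5: criterion 5 already applies at *x* > 2*b*, so there is no gap.

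| Baseline (×ULN) | Values caught only by INR (×ULN) |
|---|---|
| 0.6 | none |
| 0.75 | >3.00 to 3.75 |
| 1.0 | >3.00 to 5.00 |
| 1.5 | >3.00 to 7.50 |
| 1.75 | >3.50 to 8.75 |
| 2.0 | >4.00 to 6.00 |
| 3.0 | >6.00 to 9.00 |
| 4.0 | >8.00 to 12.00 |
| 5.0 | none |

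Section 4.1.7 admits ALT and AST up to 5×ULN, so these baselines can be enrolled.

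Both bilirubin conditions are needed. A rise from 1.2 to 2.2×ULN is only 2.2/1.2 = 1.83 times baseline, but it exceeds 2×ULN, so criterion 2 is met without INR.

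**4. Constructed example.** Baseline: ALT 1.5×ULN, bilirubin 0.5×ULN, INR 1.0. On treatment: ALT 4.0×ULN (confirmed), bilirubin 0.8×ULN, INR 1.6, no symptoms.

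- ALT ratio: 4.0/1.5 = 2.67, above 2 but not above 5. Criterion 1 fails; the enzyme part of criterion 6 is met.
- Bilirubin: 0.8×ULN is not above 2×ULN, so criterion 2 fails. 0.8/0.5 = 1.6 is not above 2, so the bilirubin route of criterion 6 fails.
- INR: 1.6 − 1.0 = 0.6, above 0.3, and 1.6 is above 1.5. The INR route is met.

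With INR measured, criterion 6 alone is met. Without it, no criterion is met.

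**5. Timing.** Accrual closed January 5, 2024. Adding 24 × 7 = 168 days gives June 21, 2024, and the +14-day visit window gives July 5. Treatment may start up to 72 hours after randomization (section 6.2.2); counting from first dose moves the last window to about July 8.

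**The case against.** The best counter-argument is that the sentence sets a floor. Section 6.2.3 calls for whatever is needed to assess the toxicity, and if bilirubin does not qualify, criterion 6 cannot be assessed without INR. Entry INR is collected, PT and INR are among the post-entry values to record, and section 8.2.1 requires a comprehensive clinical evaluation. The Manual of Procedures (MOPS), which section 8.2.1 cites for DILI guidance, may require INR. That reading is possible, but section 8.2.1 names its confirmatory tests and joins bilirubin and INR with an explicit *or*, so a site following it could reasonably stop at bilirubin. The MOPS is not available here and cannot settle the point.

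The safeguards are real. The CMC should hear of the first elevation within 48 hours, sites may consult it whether or not criteria are met, and section 9.1 allows discontinuation for drug-related toxicity. What is lost is the criteria-driven interruption, not clinical attention.

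Few cases are likely. With about 110 × 2/3 ≈ 73 participants on cenicriviroc and AURORA's rates (denominator 1180), one would expect roughly 73 × 4/1180 ≈ 0.25 adjudicated DILI cases and 73 × 45/1180 ≈ 2.8 ALT-increase events. This is rough, since the AURORA population and exposure differ and suspected DILI is broader than adjudicated DILI, but INR-only cases would be a subset of a small number.

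The timing objection also stands: SAP version 2.0 is dated July 18, 2024, after the last scheduled week 24 window.

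**Conclusion.** The concern holds. Section 8.2.1 contains a criterion that its own required tests need not evaluate, and no visible section supplies the missing INR. The affected group is narrow, as the table shows, and its frequency cannot be estimated from the documents. The effect is confined to safety monitoring: suspected DILI is not among the safety outcomes in SAP section 3.3, and no estimand or efficacy analysis changes. The conclusion rests on the protocol text alone; a MOPS requirement for INR would close the gap in practice, though not in the protocol. This should be corrected while anyone remains on treatment and becomes a low priority afterwards.

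**What to change.** In section 8.2.1, define the confirmatory tests as a repeat of the elevated enzyme(s), total bilirubin and INR, all three. Leave every threshold unchanged. This also closes the mirror gap, in which a site could measure INR and omit bilirubin at confirmation, leaving the bilirubin routes of criteria 2, 4 and 6 untested at that visit.

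The cost is a clarification letter and one PT/INR per confirmatory visit. The Schedule already provides for that test, and the baseline value is collected at entry. After the last week 24 window the change reaches only participants whose dosing is extended under section 5.1.3, and it cannot recover an INR that was not drawn. If treatment has ended, the team can still check whether INR was measured at each confirmed elevation and, where it was not, say so when reporting hepatic safety.

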8.2.2 GFR

GFR will be monitored as scheduled in [section 6.1](#).

A participant experiencing an estimated GFR <50 mL/min/1.73 m² should have the value confirmed within 14 days.

A participant who has confirmed two consecutive reductions in estimated GFR to <60 mL/min/1.73 m² may continue to participate, however the site investigator should consider dose adjustment or discontinuation of TDF and inform the participant's primary physician.

8.3 Adverse Event Related to FDG-PET/CT Imaging

Any Grade ≥3 AE that occurs due to or during the FDG-PET/CT imaging must be reported to the A5415 CMC ([contact]) within 48-72 hours after the occurrence of the AE and monitored for resolution.

8.4 FDG-PET/CT Imaging Findings

Any incidental findings in the imaging must be reviewed by the site investigator, and consult with the local radiologist designated by the site to read for incidental findings should be considered. Refer to [section 6.3.9](#) for the details regarding the requirement for a local radiologist to review all imaging. The site investigator should inform the participant and the participant's primary physician of any clinically relevant incidental finding and discuss the need for further evaluations.

8.5 Pregnancy

Participants who become pregnant after study entry must discontinue study treatment immediately. These participants should be seen for premature treatment discontinuation evaluations as per [section 6.2.4](#). These participants will also be followed on study, off study treatment through completion of the study with evaluations per [section 6.1](#), except they will not be required to fast and will not have the FDG-PET/CT imaging performed and PK samples drawn. The only safety laboratory tests that will be performed are hematology (except ANC) and LFTs. The A5415 CMC ([contact]) must be notified of any pregnancies that occur in participants on study. Management of the background ART is at the discretion of the site investigator.

Pregnancy and pregnancy outcome will be recorded on the eCRFs. Pregnancies that occur on study should be reported prospectively to The Antiretroviral Pregnancy

Registry. More information is available at www.apregistry.com. [contact]; [contact]. (For studies conducted at sites outside the United States, report to The Antiretroviral Pregnancy Registry—[contact]; [contact] or [contact].)

Pregnancy Outcomes and Reporting

If an individual chooses to discontinue from the study before the end of the pregnancy, site staff should request permission to contact them regarding pregnancy outcomes at the end of pregnancy. Once the information is obtained, pregnancy outcomes will be submitted on an eCRF at the end of the pregnancy and EAE reporting, if appropriate.

